Rapid diagnosis and management of intra-abdominal hemorrhage after blunt trauma is critical in the triage and assessment of trauma patients (1). The Focused Assessment with Sonography in Trauma examination (FAST) is an efficient, bedside, non-ionizing, non-invasive method for assessing hemoperitoneum (the presence of blood in the peritoneal cavity), in traumatically injured patients. The FAST is taught during the Acute Trauma Life Support (ATLS) Course, and is the gold standard for the initial assessment of abdominal and chest trauma (2). FASTs have excellent specificity (94.7-99.6% in most series), however sensitivity is low (20-60%) (3-5). Improving the sensitivity of the FAST would allow for earlier detection and management of life-threatening intra-abdominal hemorrhage for innumerable trauma patients.

FASTs are typically performed with the patient in the standard position, lying flat on their back. The right upper quadrant (RUQ), left upper quadrant (LUQ) and suprapubic region are scanned and evaluated for hemoperitoneum. If fluid is found in any of these views, the patient is emergently taken to the operating room (OR) to treat the intra-abdominal hemorrhage.

It has been previously shown that a standard FAST is most likely to detect hemoperitoneum in the RUQ in Morison's pouch, the space on the right side of the body that separates the liver and the right kidney (hepatorenal recess) (2). A recent pilot by Pigneri et al., compared standard FAST exam to FAST exam after the patient had been rolled onto their right side; this modified evaluation method was termed Focused Assessment with Sonography in Trauma examination after Right sided roll (FASTeR). The rationale was this position likely uses gravity to collect intra-abdominal fluid into Morison's pouch, thus making it possible to visualize small volumes of fluid that would otherwise be undetectable when the patient is lying flat (6). This study demonstrated earlier identification of intra-abdominal fluid with the FASTeR when compared to the standard FAST (6).

Rationale

All patients are rolled onto one side or the other during normal trauma evaluation. Changing practice to turn the patient onto the right side for a modified FAST, or FASTeR, can potentially increase exam sensitivity without delaying care. Our goal is to perform a large, multicenter study to evaluate the impact of FASTeR versus the standard

FAST in hemodynamically unstable trauma patients. We plan to prospectively collect data for creation of a multicenter database; enrolled subjects would undergo both the standard FAST and when appropriate (see Methods) a FASTeR. Our aim is to determine the sensitivity and specificity of the FAST and FASTeR, and determine which exam was more accurate in recognizing hemoperitoneum. Exam results will be confirmed with computed tomography (CT) imaging or operative findings.

Potential Risks and Benefits

Potential Risks

There are no expected medical risks to the study participants in excess of the normal risks of the FAST, which is minimal.

Potential Benefits

If the FASTeR is shown to detect small volumes of hemoperitoneum earlier than was previously possible with the FAST, patients may directly benefit from earlier diagnosis and treatment. Early identification of hemoperitoneum has been shown to be strongly correlated with increased survival rates (1).

Study Objectives

Primary Objective

To calculate and compare the sensitivity and specificity of detecting hemoperitoneum in the RUQ for the standard FAST and the FASTeR in the research subjects. Actual injury complex will be confirmed by CT or operative findings.

Secondary Objective

To calculate and compare the false positive rate, false negative rate, positive predictive value, negative predictive value, and positive and negative likelihood ratios for the standard FAST and FASTeR. Exam results for individual subjects will be compared to see if there is a significant difference in result accuracy.

Study Design

This is a prospective multicenter study. Detailed responsibilities for the lead (Memorial Regional Hospital) and satellite centers below.

Memorial Regional Hospital (lead)

- 1. Maintain database for enrolled MRH subjects. Data collected will include HIPAA identifiers (included in outcome measures) to monitor our own data integrity.
- 2. As lead center, MRH will aggregate and analyze collected data from satellite centers which will be submitted without HIPAA identifiers.
- 3. MRH to manage subjects meeting inclusion criteria according to our institutional patient management protocols.
- 4. MRH to adhere to IRB protocol and application as submitted.

Satellite Centers

- 1. Each center must apply and receive IRB approval from their respective IRB(s).
- 2. Each center is responsible for their own data integrity, as outlined in their approved IRB protocol and application.
- 3. Each center to provide IRB outcome or waiver letter to the lead center.
- 4. Each center to complete the data sharing agreement specific to this study.
- 5. Each center to provide care according to their institutional patient management protocols.
- 6. Each center to submit de-identified data to the lead center for analysis.

Subject Selection

Inclusion Criteria

1. Patients over 18 and under 89 years of age who present as a trauma activation with clinical history or physical signs of blunt abdominal trauma and hemodynamic instability

Exclusion Criteria

- 1. Patients under 18 and over 89 years
- 2. Pregnant women
- 3. Patients with prohibitive right sided chest trauma
- 4. Patients in extremis undergoing salvage maneuvers (chest compressions or emergent surgical intervention) which prevents performance of an ultrasound examination
- 5. Patients who leave against medical advice or are otherwise removed from the medical system before their work up has been completed

Sample Size

50 participants at MRH and 250 participants total for all sites.

Research Design

This is a prospective multicenter study, where MRH will act as the lead center. Each contributing center is responsible for obtaining IRB approval and maintaining data integrity outlined in their approved IRB protocol and application from their respective institutions. Once IRB approval has been obtained, we will begin enrolling trauma patients prospectively into a registry. The participating centers for this study represent a diverse set of trauma centers and emergency departments and include institutions with varying trauma verifications (e.g. ACS and State), sizes, geographical/metropolitan locations, and resource availability to ensure inclusivity.

Since this is a prospective observational study, data will be collected prospectively without altering the manner in which the patients are managed by the surgeon and institution. Accordingly, an informed consent waiver is requested. Patients will be given a flyer with information about the study (see additional documents). Data will be collected for a two year period with interim analysis when specific enrollment targets are met. All data will be recorded on a data sheet and transferred to a secured database (REDCap) without patient identifiers.

Patients with clinical history or physical signs suspicious for blunt abdominal trauma will undergo the standard FAST in the emergency department as per ATLS protocol. During the secondary survey, all patients are rolled for examination of their back and removal of the rigid spine board, per ATLS. In our study, we will standardize this practice so that all patients are rolled onto their right side for this portion of the examination. Patients with extensive right sided chest trauma will be excluded at the discretion of the Trauma Surgeon. After the right sided roll to remove the back board, a repeat ultrasound examination of the RUQ will be performed.

All participating centers, including MRH, will collect and submit the following data to the database for each enrolled subject: age, gender, initial trauma bay vital signs, mechanism of injury, results of the FAST, results of the FASTeR, and injury complex as confirmed by CT imaging or operative findings for their respective centers. Both the CT scan and any surgical intervention that the participant undergoes as a study subject will be performed through routine standard of care procedures. The database will not contain HIPAA identifiers

MRH will record our internal subject medical record numbers and dates of admission to verify data fields and monitor our own data integrity. All data will be de-identified prior to publication.

Study Outcome Measures (Endpoints)

The study outcome measures will be recorded using the "Multicenter Study: Can we be FASTeR? A multicenter study utilizing Right sided roll to improve sensitivity of the FAST examination" data collection form. The patient medical record number (MRN) will be

recorded by hand on the tool for all MRH enrolled subjects only; subject data will be cross-checked with the electronic records in order to maximize data integrity.

- 1. Number of patients admitted and discharged from MRH between the timeframe (October 16, 2017- October 16, 2019) who present as a trauma activation with clinical history or physical signs of blunt abdominal trauma and hemodynamic instability
 - a. MRN (recorded by hand), internal use only
 - b. Admission date (recorded by hand), internal use only
- 2. Demographics (e.g. age, gender)
- 3. Admission vital signs (e.g. heart rate [bpm], blood pressure, respiratory rate, oxygen saturation)
- 4. Results (positive or negative) of the FAST (RUQ, LUQ, surprapubic)
- 5. Results of the FASTeR (RUQ)
- 6. Method where final injury complex determined (if applicable)
 - a. Operative findings
 - b. CT scans
 - c. Other imaging (e.g. MRI, x-ray, ultrasound)
- 7. Final injury complex (if applicable)
 - a. Liver injury
 - b. Splenic injury
 - c. Gastrointestinal injury (type)
 - d. Genitourinary injury (type)
 - e. Vascular/mesenteric injury (type)
 - f. Pancreatic injury
 - g. Other (type)
- 8. Outcome of hemoperitoneum confirmed by imaging or operative findings

Statistical Analysis Plan

All subjects who meet inclusion criteria and have complete data available will be used for data analysis. The sensitivity and specificity (with confidence intervals) for detecting hemoperitoneum using the standard FAST or the FASTeR versus the actual injury complex findings (CT or operative findings) will be calculated in the research subjects along with the false positive rate, false negative rate, positive predictive value, negative predictive value, and positive and negative likelihood ratios. A McNemar's test will be used to directly compare the accuracy of the FAST and FASTeR results for individual research subjects.

The data pooled from the participating centers will provide a robust data set that will minimize center or physician specific result bias and provide the needed statistical volume as calculated by the power analysis.

Study Procedures

Subject Identification, Recruitment, and Screening

This a prospective multicenter study, which will prospectively record data without altering the manner in which the patients are managed by the surgeon and institution. Accordingly, an informed consent waiver is requested. All data will be recorded on a data sheet and transferred to a secured database (REDCap) without patient identifiers.

Eligibility for study enrollment will be considered for all patients presenting to MRH as a trauma alert during the study period, with a clinical history or physical signs for blunt abdominal trauma who would clinically indicate a standard FAST in the trauma bay as per ATLS protocol. Patients with extensive right sided chest trauma will be excluded at the discretion of the Trauma Surgeon. Both the CT scan and any surgical intervention that the participant undergoes as a study subject will be performed through routine standard of care procedures.

Study Duration

We anticipate a rolling accruement of subjects over a two year period. A sample size calculation (power analysis) was performed to estimate the needed total participant accruement to provide a power of 90% and an alpha of <0.05. Standard FAST should identify up to 60% of subjects with significant intra-abdominal injury. If we assume that the FASTeR will identify hemoperitoneum in 1 of 4 subjects with intra-abdominal injury and previous negative FAST examination, then our needed sample size is 209 subjects. To account for subjects meeting exclusion criteria, we will plan to accrue 250 patients. Given that this sample size calculation was based on estimation regarding the sensitivity of the FASTeR in this patient population, interim analyses regarding primary endpoint will be conducted after 100 subjects have been accrued and again after 200 subjects have been accrued. Subject charts will be reviewed in increments of ten as they are enrolled.

Withdrawal of Subjects

Subjects that are unable to tolerate the position changes described in the protocol will be considered screening failures and will be automatically withdrawn from the study.

Subjects that receive the FASTeR are free to withdraw themselves from the study at any time. They may withdraw from the study by notifying the PI, [name], directly by phone. The option to withdraw and the contact information for [name] are listed on the study information flyer that will given to all subjects.

Quality Control and Quality Assurance

Study data will be collected and managed using REDCap electronic data capture tools. REDCap (Research Electronic Data Capture) is a secure, web-based application designed to support data capture for research studies, providing 1) an intuitive interface for validated data entry; 2) audit trails for tracking data manipulation and export procedures; 3) automated export procedures for seamless data downloads to common statistical packages; and 4) procedures for importing data from external sources (7).

Satellite centers are responsible for getting IRB approval and maintaining their own data integrity as outlined in their respective IRB protocols and applications. The lead center (MRH) will aggregate and analyze deindentified data collected in REDCap.

Ethical Considerations

This study is to be conducted according to US and international standards of Good Clinical Practice, applicable government regulations and Institutional research policies and procedures.

This protocol and any amendments will be submitted to a properly constituted Institutional Review Board (IRB), in agreement with local legal prescriptions, for formal approval of the study conduct.

Confidentiality and Privacy

Information about study subjects will be kept confidential and managed according to the requirements of the Health Insurance Portability and Accountability Act of 1996 (HIPAA). Subjects may voluntarily withdraw from the program or revoke their authorization to share information related to the research. In the event that a subject revokes authorization to collect or use PHI, the investigator, by regulation, retains the ability to use all information collected prior to the revocation of subject authorization.

Subjects will be assigned a study identification (ID) number that will distinguish subjects; a master code list linking the subject's study ID to patient identifiers will not be shared and will be stored in a separate location from the study data. All data collected will be deidentified and aggregated before sharing. The master code list and study data and will be destroyed following data analysis and study completion. All data will be de-identified prior to publication.

Conflict of Interest

There is no conflict of interest.

Funding Source

None

Publication Plan

The Investigator intends to publish the results of this prospective study in a peerreviewed journal at an unspecified time in the future. The Investigator will serve as the primary and corresponding author for any future publications related to this proposed study.

References

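### The study is sized on what FASTeR adds after a negative FAST, but neither that yield nor the accuracy of FAST followed by FASTeR is a planned output

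*Combined protocol and SAP*

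**What the plan says.** The Primary Objective is "To calculate and compare the sensitivity and specificity of detecting hemoperitoneum in the RUQ for the standard FAST and the FASTeR". The Rationale frames the aim the same way, as to "determine which exam was more accurate in recognizing hemoperitoneum". The Statistical Analysis Plan calculates accuracy measures for each exam separately against CT or operative findings, and adds: "A McNemar's test will be used to directly compare the accuracy of the FAST and FASTeR results for individual research subjects".

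The procedure is sequential. The Rationale says that "enrolled subjects would undergo both the standard FAST and when appropriate (see Methods) a FASTeR". Under Research Design the standard FAST comes first, and then: "After the right sided roll to remove the back board, a repeat ultrasound examination of the RUQ will be performed". In Study Outcome Measures, item 4 reads "Results (positive or negative) of the FAST (RUQ, LUQ, surprapubic" and so covers three views. Item 5 records FASTeR in the RUQ only.

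Study Duration bases the sample size on the assumption that "FASTeR will identify hemoperitoneum in 1 of 4 subjects with intra-abdominal injury and previous negative FAST examination". The opening background section says of the standard exam: "If fluid is found in any of these views, the patient is emergently taken to the operating room".

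The objectives, outcome list and Statistical Analysis Plan define no combined result (positive on FAST or on FASTeR). None of them names FASTeR's yield among FAST-negative subjects as something to be reported.

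**The concern.** A one-view scan done after a three-view exam, and justified by what it finds when that exam was negative, is an add-on test. Its value is the true positives and false positives it contributes beyond FAST. The planned comparison treats the two exams as competitors, which is a different quantity.

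A subject with hemoperitoneum who is FAST-positive and FASTeR-negative counts against FASTeR head to head. Under a FAST-then-FASTeR reading nothing is lost, because FAST already showed the fluid. Such subjects can cancel a real added yield.

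The opposite error is possible if the words on the RUQ in the Primary Objective mean that FAST is scored on its RUQ view alone. Fluid already seen in the LUQ or suprapubic view, and then on FASTeR, would count as a FASTeR gain.

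On specificity, two exams with equal rates show no head-to-head difference, yet calling either one positive can still raise the false-positive rate. At stake is whether the study can report the gain it was sized on, and what that gain costs.

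**Working it through.** **The plan's own figure.** Study Duration gives FAST 60%, 1 in 4 of the remainder found by FASTeR, 90% power, alpha 0.05 and n = 209. For the planned paired test, the gain is p10 = 0.25 × 0.40 = 0.10. With no losses (p01 = 0) and a two-sided test:

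n = (1.960 × √0.10 + 1.282 × √0.09)² / 0.10² = 100.9, so 101 subjects with hemoperitoneum (82 one-sided).

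This does not reproduce 209. Other choices come close. A one-sided one-sample comparison of 60% with 70%, using the null variance, gives 206. McNemar with gains of 0.15 and losses of 0.05 also gives 206. The documents do not state the method, sidedness, discordance or prevalence, so I draw no conclusion about 209, and the point does not depend on it.

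**Sensitivity.** Let s be FAST sensitivity: up to 60% in Study Duration, 20-60% in the background section. Let r be the share of FAST-positive subjects with hemoperitoneum in whom FASTeR is also positive; the documents do not give it. Study Duration speaks of intra-abdominal injury, and I take those subjects as the ones with hemoperitoneum (an assumption). The 1-in-4 yield is held fixed.

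- Added yield = 0.25 × (1 − s)
- FAST-then-FASTeR = s + 0.25 × (1 − s)
- FASTeR alone = 0.25 × (1 − s) + s × r
- Break-even r (FASTeR alone equals FAST) = 1 − 0.25 × (1 − s) / s

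| FAST sensitivity | Added yield | FAST-then-FASTeR | FASTeR alone | Break-even r |
|---|---|---|---|---|
| 60% | 10 points | 70% | 10 + 60r % | 0.833 |
| 40% | 15 points | 55% | 15 + 40r % | 0.625 |
| 20% | 20 points | 40% | 20 + 20r % | 0 |

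At 60%, FASTeR alone is 70% for r = 1, 64% for r = 0.90, 60% for r = 0.833 and 55% for r = 0.75. The added yield is 10 points in all four cases.

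The effect on the head-to-head test at 60% follows from p01 = 0.60 × (1 − r). With r = 0.95, p01 = 0.03 and the McNemar formula n = (1.960 × √(p10 + p01) + 1.282 × √(p10 + p01 − (p10 − p01)²))² / (p10 − p01)² gives 275 subjects with hemoperitoneum. With r = 0.90, p01 = 0.06 and it gives 1,047. With r = 1 it gives 101.

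**Specificity.** The background section quotes 94.7-99.6% for FAST. No figure is given for FASTeR, so I assume the same range.

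- Independent false positives: 0.947² = 0.897 and 0.996² = 0.992. Combined specificity is 89.7-99.2%, a loss of 5.0 to 0.4 points.
- Fully shared false positives: combined specificity stays at 94.7-99.6%, with no loss.

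The head-to-head difference is zero in both cases, so the planned comparison cannot tell them apart.

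**Precision of the added yield.** If all 209 subjects had hemoperitoneum, about 21 would be added detections: 21/209 = 10.0%, 95% Wilson interval 6.7% to 14.9%. The documents give no prevalence; fewer subjects with hemoperitoneum would widen the interval.

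**The case against.** The strongest reply is that any paired accuracy study does both exams in some order, and here the order follows from when patients are rolled. Comparing the RUQ before and after the roll is a fair test of the gravity rationale in the background section. This stands: the present comparison answers a legitimate question and should be kept.

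A reader might infer that sites would adopt FAST followed by FASTeR, and so that the plan studies the wrong strategy. The documents do not say this. The Rationale speaks of a modified FAST, centers follow their own management protocols, and no algorithm for acting on a FASTeR result is given. Add-on is the natural reading because FASTeR covers only the RUQ and follows FAST, but it remains a reading.

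It can also be said that the paired table already holds the answer, since its FAST-negative, FASTeR-positive cell among subjects with hemoperitoneum is the numerator of the added yield. That is correct. The gap is in what is pre-specified and reported, not in what is collected.

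A reader might infer that the head-to-head result will probably hide or reverse a true benefit, or that false positives will nearly double. Neither follows. The values of r have no source, the reversal is easiest at the 60% ceiling, and repeat scans of the same site in the same patient need not err independently. The r model also assumes that every FAST-positive subject gets a FASTeR. FAST-positives may go straight to surgery, FASTeR is done when appropriate, and only complete data are analyzed, so how often a FAST-positive, FASTeR-negative pair would be observed is unknown.

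Finally, a co-primary superiority test on combined sensitivity would be poor, because an either-positive rule cannot be less sensitive than FAST. This objection stands and shapes the fix.

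**Conclusion.** The mismatch is real. The sequence of exams and the sizing assumption are add-on, while the objectives and Statistical Analysis Plan only set one exam against the other. The study therefore does not plan to report the quantity it was sized on.

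For sensitivity, the two quantities coincide only if FASTeR repeats every FAST-positive finding (r = 1), which the documents do not state. Below that, FASTeR alone understates the combined sensitivity by s × (1 − r). For specificity, the unmeasured cost runs from zero to about 5 points, if FASTeR shares FAST's quoted specificity. These sizes rest on equating injury with hemoperitoneum, on a fixed 1-in-4 yield, and on unsourced values of r and error dependence.

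The documents do not support saying that the study is invalid, that the data are inadequate for the add-on question, or that 209 is wrong. This is a worthwhile and inexpensive addition to the plan.

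**What to change.** Keep the present primary comparison. In Study Objectives and the Statistical Analysis Plan, pre-specify a key secondary analysis, not a co-primary, of three-view FAST (any view positive) against FAST-then-FASTeR (any FAST view or FASTeR positive). Report:

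- the gain in sensitivity and the loss in specificity, each with a confidence interval, and no superiority test on sensitivity, since that difference cannot be negative;
- among subjects negative on all three FAST views, the number and proportion of true positives and of false positives that FASTeR adds;
- the number of FAST-positive subjects who did not get a FASTeR, and whether the complete-data rule removes them. Their combined result is already positive, so their handling affects the estimates.

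Any conclusion about adding FASTeR to FAST should cite this analysis.

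The cost is wording and a little more analysis. Items 4, 5 and 8 of Study Outcome Measures already supply the data, and because the analysis is secondary the two interim looks at the primary endpoint are unaffected. The downside is a combined specificity that can only equal or fall below that of FAST alone.

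### FASTeR is always the later, repeat RUQ scan, so a gain over FAST cannot be credited to the right-sided roll as the form title and rationale imply

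*Combined protocol and SAP*

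**What the plan says.** **Order.** Research Design has the standard FAST done first, in the emergency department. Then: "During the secondary survey, all patients are rolled for examination of their back and removal of the rigid spine board, per ATLS". The study standardizes this roll to the right, after which "a repeat ultrasound examination of the RUQ will be performed". No other order appears. The power assumption under Study Duration is likewise conditional on an earlier negative FAST.

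**What is recorded.** Study Outcome Measures (Endpoints) lists FAST results by region, the FASTeR result for the RUQ, demographics, vital signs, how the injury was determined, the injury complex and confirmed hemoperitoneum (item 8). It lists no scan time, operator or masking status. On data handling, Research Design says "All data will be recorded on a data sheet and transferred to a secured database (REDCap) without patient identifiers" and Study Duration says "Subject charts will be reviewed in increments of ten as they are enrolled". Neither says when a scan result must be written down relative to CT or surgery.

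**Analysis.** The Statistical Analysis Plan compares the paired results with McNemar's test, with no term for order or elapsed time.

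**Where the roll is credited.** The data collection form's title speaks of "utilizing Right sided roll to improve sensitivity of the FAST examination". The opening background offers gravity pooling fluid in Morison's pouch as the likely mechanism. The Rationale says patients are already rolled to one side or the other, and proposes the right side as the change in practice.

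**The concern.** The two scans differ in more than position. The second is also a repeat look at the same quadrant and is made later, in patients selected for hemodynamic instability, in whom more fluid may have collected. Nothing in the design or analysis separates these explanations.

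This matters because the practice question is the right side itself. If looking again a little later explains the gain, a report crediting the roll would recommend the wrong element of the sequence.

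A secondary risk concerns when results are written down. With no rule or record on this, a scan field could be completed after the CT or operative result is known, which would pull that scan toward the reference.

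**Working it through.** **1. What differs between the scans.**

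| Feature | FAST | FASTeR (RUQ) | Separated by the plan? |
|---|---|---|---|
| Position | supine | after right roll | this is the question |
| Look | first | repeat | no: no supine repeat |
| Time | earlier | secondary survey | no: no interval set, no times recorded |
| Operator and prior knowledge | not stated | not stated | no: no operator field, no masking described |

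The confounding follows from the fixed order alone.

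**2. The plan's expected gain.** Inputs from Study Duration: FAST identifies up to 60% of injured subjects, and FASTeR finds 1 in 4 of those FAST missed.

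Gain = (1 − 0.60) × 0.25 = 0.40 × 0.25 = 0.10. Sensitivity rises from 0.60 to 0.70 if no FAST positive is lost.

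**3. The part due to position.** Let r be the share of FAST misses that a plain repeat scan would find. The documents give no value, so 5% to 20% is assumed. Part due to position = 0.40 × (0.25 − r).

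| r (assumed) | Due to repeat scan | Due to position |
|---|---|---|
| 5% | 2 points | 8 points |
| 10% | 4 points | 6 points |
| 15% | 6 points | 4 points |
| 20% | 8 points | 2 points |

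The 10-point total depends on 60% FAST sensitivity. At 20%, the lower end of the background's range, it would be 0.80 × 0.25 = 20 points. The fraction due to position, 1 − r/0.25, does not depend on FAST sensitivity: it runs from 80% at r = 5% to 20% at r = 20%.

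**4. What McNemar's test would show if the roll did nothing.** Suppose a repeat look alone finds a share q of injured FAST-negative subjects. FASTeR-only detections then occur in 0.40 × q of injured subjects. If no FAST positive is lost, a two-sided exact test at 5% needs at least 6 discordant pairs, all favoring FASTeR (2 × 0.5^6 = 0.031; with 5 pairs, 0.0625). The table gives the chance of a significant result for FASTeR. Figures in brackets apply if FASTeR also misses 2% of injured subjects whom FAST found.

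| q (assumed) | 100 injured | 209 injured |
|---|---|---|
| 5% | 1.5% (0.3%) | 24% (1%) |
| 10% | 21% (4.5%) | 85% (14%) |
| 15% | 56% (17%) | 99% (46%) |
| 25% | 94% (56%) | about 100% (92%) |

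The number injured is not stated in the plan. The value 100 is a round assumption, and 209 treats the whole stated sample size as injured.

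**5. How many informative detections to expect.** On the plan's assumptions, FASTeR-only detections number 0.10 × 100 = 10, or 0.10 × 209 ≈ 21.

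**6. The stated sample size.** The planned test with the stated inputs gives, at 90% power and two-sided 5%, (1.960 × √0.10 + 1.282 × √(0.10 − 0.01))² / 0.01 ≈ 101 injured subjects, not 209. Sidedness, discordance and injury prevalence are unstated, so this does not show 209 to be wrong, and the present point does not rest on it.

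**The case against.** The strongest reply is that the order is a sensible pragmatic choice. It follows the trauma workflow in an observational study, and whether a scan after the roll adds detections is a legitimate question that this design can answer. That stands: the accuracy of the sequence as performed remains estimable.

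It is also true that the stated aim does not credit position. A reader might infer that it does, but it is only to "determine which exam was more accurate in recognizing hemoperitoneum", and the Primary Objective likewise compares exams. The causal credit sits in the form title and in the background, where the mechanism is hedged.

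Two other stronger readings go too far:

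- **The FASTeR operator knows the FAST result.** This is plausible, since the background says "If fluid is found in any of these views, the patient is emergently taken to the operating room", so the treating team knows a positive result. But no text says who performs FASTeR or what that person knows. Only the absence of described masking is documented.
- **Scan fields are filled in after CT or surgery.** The documents describe prospective recording. Reviewing charts in tens does not mean results are first entered then. Late entry is an uncontrolled risk, not a documented practice, and its effect on the paired comparison is not quantified here.

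Finally, the repeat-scan yield is assumed, so the split in points is illustrative. Time and operator fields describe the confounding without removing it, and 10 to 20 detections are too few to divide finely. All of this stands, which is why the narrower conclusion comes first among the fixes.

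**Conclusion.** The point holds in a limited form. As planned, a gain for FASTeR cannot be separated from a second look or from fluid accumulating between scans, so it cannot be credited to the right roll. That conclusion needs no numerical assumption.

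Its size is unknown from the documents. With 60% FAST sensitivity, one in four misses found and no FAST positive lost, 8 to 2 of the 10 points would be due to position for an assumed repeat-scan yield of 5% to 20%. The chance of a significant result with no roll effect ranges from negligible to near certain, depending on that yield, the number injured and any FAST positives lost.

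**What to change.** 1. **Wording.** State the objective and conclusion as the incremental yield of a repeat RUQ scan after the right roll, not as an effect of position.
2. **Time and operator.** Add clock time and operator role for each scan to the data sheet. Report FASTeR-only detections descriptively by interval and by same or different operator. Note that about 10 to 20 are expected and that this does not remove the confounding.
3. **Timing of entry.** Record on the sheet whether each scan result was written down before the CT or operative result was known. Add a sensitivity analysis that flags later entries and notes that they may cluster in patients taken quickly to surgery, so that simply dropping them could select patients. Take item 8 from the CT report or operative note without reference to the scan fields.

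The cost is a few form fields, some added recording at each site and a more modest claim. No extra scan is needed. Times and operators may not be recoverable later, so the fields need to be on the sheet when the scans are done.
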